8.6. Data Management

A data management plan (DMP) will be created and will describe all functions, processes, and specifications for data collection, cleaning and validation for the DUS. High data quality standards will be maintained and processes and procedures utilized to repeatedly ensure that the data are as clean and accurate as possible when presented for analysis. Data quality will be enhanced through a series of programmed data quality checks that automatically detect out-of-range or anomalous data at the time of data entry.

8.6.1. Data Entry for DUS / Electronic Data Capture

Each patient will be uniquely identified in the study by a patient identification number.

All data captured at sites will be collected and entered directly by physician (or designee) into the secure internet-based eCRF. All sites will be fully trained on using the eCRF. The eCRF users will be able to access their account with a personalised username and password. All eCRFs should be reviewed, electronically signed, and dated by the investigator (or designee). An adequate explanation should be documented for all

Page 125

2013N177706 00 WEUKBRE7133

changes or corrections to eCRFs. Each site will only have access to the patient data entered by the individual site through the eCRF.

8.6.2. **Source Documents**

In most cases, the source documents will be contained in the patient's medical record and data collected in the eCRF must match the data in the medical records. All original source documentation is expected to be stored at the site for the longest possible time as required by local applicable regulations or as specified in the contract, whichever is longer. The site will be instructed to notify GSK before any destruction of medical records of study participants.

8.6.3. File Retention and Archiving

To enable audits from regulatory authorities or GSK, the investigator must agree to keep records, including the identity of all participating patients, all original signed informed consent forms (ICFs), patient screening logs, copies of all eCRFs (which will be provided by sponsor at study end), source documents and adequate documentation of relevant correspondence. The records should be retained by the investigator. The records must be available for review in the event the site is selected for monitoring, audits, or inspections and must be safely archived following the study conclusion, according to local regulations or as specified in the contract, whichever is longer. In the event that archiving of the file is no longer possible at the site, the site will be instructed to notify GSK.

8.7. **Data Analysis**

8.7.1. **DUS Analyses**

This is a multinational, retrospective, observational, medical chart review study. A Statistical Analysis Plan (SAP) describing the detailed statistical methodology and analysis will be provided as a separate document.

Continuous variables will be reported as mean, standard deviation, median and range. Categorical variables will be summarised as number and proportion of the total study population (counting missing data as a class), and by subgroups if and where appropriate. Confidence intervals (as 95% CI) will be calculated using the method outlined by Newcombe (Newcombe, 1998) for the key variables.

Participating physicians

Number of participating physician, and practice setting, will be summarized descriptively.

Page 126

Patient demographics and disease characteristics

Descriptive statistics will be given for the variables below:

- Age at time of initial REVOLADE prescribing dose
- Gender
- Race/Ethnicity
- Relevant medical history for applicable conditions

REVOLADE Patient characteristics

Number and percentage of the following categories will be described and stratified if number permits according to the dates of new indication approval:

- Adult chronic ITP patients
- Adult patients with HCV and clinically meaningful thrombocytopenia
- Patients < 18 years with chronic ITP
- Patients < 18 years with HCV (with and without thrombocytopenia)
- Patients < 18 years without chronic ITP or HCV but with another disease type, by specific disease type
- Adult patients with cancer, by cancer type
- Adult patients with myelodysplastic syndrome/AML
- Adult patients receiving surgery during the observation period
- Adult patients in any other disease groups, by specific disease type

REVOLADE Utilisation characteristics

Descriptive statistics will be given for the variables below:

- Duration of REVOLADE treatment, stratified by the categories described above (if numbers permit)
- Initial dose (25 mg, 50 mg or other)
- Dose changes
- Rationale for dose changes
- Reason for temporary or permanent discontinuation

Platelet count characteristics

Descriptive statistics will be given for the variables below:

- Platelet count (x10⁹/L) at the time of primary medical condition, at initiation of REVOLADE, overall and by indication and by initial starting dose
- Platelet count resulting in dose change, by dose

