8.2.3. Study Duration

The eligibility period begins within the period immediately after REVOLADE has been launched in a given country (for instance, REVOLADE launch dates for the chronic ITP indication are in Germany, France and Spain, April 2010, January 2011, and December 2010, respectively) until the index date chosen as the start date of data abstraction i.e., September 2014 (Figure 1).

The observational period for each patient is the interval between the first dose of REVOLADE and the last dose if discontinued before September 2014. If a patient stops and re-starts REVOLADE during the observation period, all repeated treatment intervals will be captured. Also, if the patient is still on REVOLADE at the end of the study period, September 2014, then the observation period is between first dose and September 2014.

The planned duration of the study is approximately 14 months after the inclusion of the first patient. This period takes into account 8 months of data collection and study start-up and a 6 month period between last patient in and final study report.

GSK will closely monitor inclusion rates. If projected recruitment rates indicate that patient targets may not be achieved in the planned recruitment period, consideration will be given to extending the recruitment period, initiating additional sites within the three existing countries, and/or expanding the study into additional EU countries.

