8.3.3. REVOLADE Exposure during Observational Period

- REVOLADE exposure
 - Start date
 - o Stop date if recorded
 - Hospital discharge date (if hospitalized)
 - o Doses administered (including all changes in dose)
- Indication for REVOLADE
- If REVOLADE discontinued, date and reason for discontinuation

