8.9. Limitations of the Research Methods

Potential limitations of the study design and measures proposed to address them include enrolment bias. To address this, sites will be expected to consecutively enrol eligible subjects and to maintain screening logs of all subjects meeting eligibility criteria, along with reasons for non-enrolment.

The Marketing Authorization Holder will closely monitor the enrolment rates. If projected enrolment rates indicate that patient targets may not be achieved within the planned enrolment period, consideration will be given to initiate additional sites within the participating countries, and/or to expand the study into additional EU countries.

Data collection will be initiated following the study-defined abstraction starting date. Initiation of selection of patient records meeting study selection criteria will commence on or following this date- September 2014. Data on drug utilisation will be censored from then and not considered in the analyses. This approach will ensure that study procedures do not influence prescribing practices.

A number of measures will also be implemented to ensure the completion of the drug utilisation questionnaire is conducted in a systematic, professional, and unbiased manner:

- Programming of the EDC version of the questionnaire (eCRF) will be reviewed by a quality control process and simulation prior to implementing the questionnaire
- Standard scripts will provide consistent instruction on completion of the questionnaire All individuals performing abstraction of data from medical records will be trained on appropriate data abstraction techniques

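### Treatment duration is cut off at September 2014 for patients still on drug, but the planned mean, SD, median and range ignore this and understate it

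*Protocol*

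**What the plan says.** Under the utilisation characteristics in Protocol section 8.7.1, "Descriptive statistics will be given for the variables below", and the list opens with "Duration of REVOLADE treatment, stratified by the categories described above (if numbers permit"). The same section fixes the form of such statistics: "Continuous variables will be reported as mean, standard deviation, median and range". It makes no exception for duration.

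Section 8.2.3 sets the observed interval. For a patient who stopped before September 2014 it runs from first dose to last dose. For a patient whose treatment continues past the cut-off, "then the observation period is between first dose and September 2014". It adds that all repeated intervals are captured if a patient stops and re-starts. Section 8.9 says of the period after the cut-off: "Data on drug utilisation will be censored from then and not considered in the analyses". Section 8.3.3 collects the start date, "Stop date if recorded", and the date and reason for any discontinuation.

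Section 8.2.5 accepts first prescriptions from national launch up to September 2014, so a patient may enter shortly before the cut-off. The protocol gives no time-to-event summary, no count of patients still on treatment, and no rule for the duration of an ongoing course. Sections 8.7.1 and 8.7.3 leave detailed methods to a SAP.

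**The concern.** For a patient still on drug in September 2014, the time since first dose is a right-censored value: true duration is at least that long. A mean or median that treats it as a finished course is too low. Dropping ongoing patients does not help, because short courses are the ones most likely to have ended before the cut-off.

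The amount of understatement depends on how long each group could be observed, and the tables split patients along lines where that differs. Section 8.7.3 presents results per country as appropriate, and launch dates differ by country. Section 8.7.1 stratifies duration by diagnosis and age category, and post-approval HCV use could start only from September 2013. Section 8.7.1 also splits the patient categories by indication approval date if numbers permit. If that split carries into the duration table, every group starting after September 2013 has at most about 12 months, whatever the diagnosis. Groups with equal persistence could then show different durations. Utilisation patterns are the subject of the first study objective (section 7).

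**Working it through.** The protocol states no duration and no share still on treatment, so there is no figure of its own to reproduce.

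**Windows, from the dates in section 8.2.5**
- Germany, April 2010 to September 2014: 4 × 12 + 5 = 53 months.
- Spain, December 2010 to September 2014: 4 × 12 − 3 = 45 months.
- France, January 2011 to September 2014: 3 × 12 + 8 = 44 months.
- Post-approval HCV use, September 2013 to September 2014: at most 12 months.

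**Assumptions, not in the documents.** Starts are uniform over a window of w months. True duration T is exponential with median m, so λ = ln 2 / m. The plan records X = min(T, time to cut-off).

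**Formulas**
- P(X > x) = exp(−λx) × (1 − x/w). The reported median solves this for 0.5.
- Share still on drug at cut-off = (1 − exp(−λw)) / (λw).
- Reported mean / true mean = 1 − that share (exponential case).

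**Results for the median**

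| Window w | True median m | Reported median | P(X > x) there | Still on drug |
|---|---|---|---|---|
| 53 | 12 | 8.8 | 0.602 × 0.834 = 0.50 | 0.953 / 3.061 = 31% |
| 44 | 12 | 8.4 | 0.616 × 0.809 = 0.50 | 0.921 / 2.542 = 36% |
| 53 | 24 | 13.6 | 0.675 × 0.743 = 0.50 | 0.784 / 1.531 = 51% |
| 12 | 12 | 4.3 | 0.780 × 0.642 = 0.50 | 0.500 / 0.693 = 72% |

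**Range for the mean** (simulation, 400,000 draws per case; reported mean as a fraction of true mean)

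| True duration | 44 to 53 months | 12 months |
|---|---|---|
| Exponential, mean 6 | 0.86–0.89 | 0.57 |
| Exponential, mean 12 | 0.73–0.78 | 0.37 |
| Exponential, mean 24 | 0.54–0.60 | 0.21 |
| Exponential, mean 36 | 0.42–0.48 | 0.15 |
| Uniform, 1–3 months | – | 0.91 |
| Uniform, 4–8 months | – | 0.74 |
| Uniform, 9–15 months | – | 0.50 |

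Every case is below 1.

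**Completed courses only.** With w = 53 and a true mean of 24 months, the mean over completed courses is 12.2 months. Counting ongoing patients to the cut-off gives 14.4. Restricting to completed courses makes the bias worse here.

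**Kaplan-Meier on the same data.** With w = 53 and a true mean of 24, it gives a median of 16.7 months (true 16.7), against 11.1 for the plain median. With w = 12 and a true mean of 6, it gives 4.2 (true 4.2), against 2.7. With w = 12 and a true exponential mean of 24 or more, the median is not reached.

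**The case against.** The strongest reply is that this is SAP detail. The mean/SD/median/range sentence is a general default, section 8.9 already uses the word censored, and nothing forbids adding a time-to-event summary. That is fair as far as it goes, and the SAP is not at hand. But the protocol is not silent: it names a summary, applies it to duration without exception, and that summary does not suit a censored variable.

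A second reply is that section 8.3.3 concerns exposure during the observational period, so a plain summary is a correct description of observed exposure. This stands if the table says so. Section 8.7.1 calls the variable duration of treatment, and a reader would take it as that.

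A reader might infer that HCV duration is the most severely understated. The documents do not support that ranking. The 12-month limit covers only post-approval use, whereas section 8.3.4 provides for HCV use before approval, classed as off-label, which can be observed for longer. The order also depends on unknown true durations. At an equal true mean of 12 months, HCV fares worse (0.37 against 0.73–0.78). If HCV courses last 4–8 months (0.74) and ITP use averages 24–36 months (0.42–0.60), the order reverses. Section 8.2.5 expects very few HCV patients, duration is stratified only if numbers permit, and no formal contrast of ITP with HCV duration is planned.

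It is also fair that duration is one of several descriptive variables and does not bear on the off-label proportion behind the sample size in section 8.5.1.

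**Conclusion.** The point holds. Followed as written, section 8.7.1 understates treatment duration whether ongoing patients are counted to September 2014 or left out, and groups with different windows are not directly comparable. The direction follows from the cut-off itself. One thing could pull the other way: a patient who stopped without a recorded stop date and is then counted as ongoing.

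The size is illustrative. Under uniform starts and exponential discontinuation, a true median of 12 months is reported as about 8.8 in a 53-month window and 4.3 in a 12-month window. The loss is small if courses are short relative to the window. No ranking of indications is established. Importance is moderate: the change should be made, but the off-label estimate does not depend on it.

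**What to change.** In section 8.7.1, estimate time from first dose to discontinuation by Kaplan-Meier, overall and by category where numbers permit, with patients still on drug censored at the September 2014 cut-off. Report:
- the median with 95% CI, or 'not reached';
- the proportion still on treatment at fixed times that lie within each group's window;
- the number still on treatment at the cut-off.

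State how stop and re-start intervals count, and how a missing stop date is handled, since section 8.3.3 allows for one.

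If mean, SD, median and range are kept, give them for all patients under the label 'observed exposure to September 2014'. Do not offer figures for completed courses only as an estimate of duration.

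The cost is wording and a little extra analysis, using dates the eCRF already requests. The Kaplan-Meier median may not be reached in short-window groups. The method also assumes that persistence does not vary with start date, which the report should mention.

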8.7.2. Handling of Missing Data

In general, missing data will not be imputed and will be analyzed as they are recorded in the study CRF.

Page 127 WEUKBRE7133

The proportion of missing data will be reported for each measured variable in the study.

8.7.3. General Considerations

All computations and generation of tables, listings and figures will be performed using SAS 9.1.3 or higher (SAS Institute, Cary, NC, USA) statistical software.

The analysis methods will be fully described in a SAP written and finalised before database lock. Data will be presented for the whole study population and per country (as appropriate).

8.8. Quality Control

This study will be outsourced to a CRO, selected in accordance with GSK standard operating procedures (SOPs). The study will be performed by the CRO, with guidance, input, review and approval of GSK, including development of materials, recruitment, training and management of sites, site monitoring, electronic data capture (EDC) and data management and analysis.

8.8.1. Site Monitoring

During the site initiation visit, the monitor will provide training on the conduct of the study to the investigator, and all site staff involved in the study. In order to ensure the integrity of the data, sites will be monitored. A risk based monitoring approach will be conducted during the study with remote and ad hoc on site monitoring that will be performed to examine compliance with the protocol and adherence to the data collection procedures, to assess the accuracy and completeness of submitted data, and to verify that records and documents are being properly maintained for the duration of the study. The monitor will perform source data verification by review of original patient records. The investigator will allow the monitor to have direct access to appropriate parts of patients' medical records relating to their participation in this study, for the purpose of verifying the data submitted by the site.

The monitor will close out each site after the last patient's data collection is completed, all data have been entered and all outstanding monitoring issues have been resolved or addressed.

Representatives of GSK and Competent Authorities must be permitted to inspect all study-related documents and other materials at the site, including the Investigator (Investigator) Site File, the completed eCRFs and the patients' original medical records. Inspections may be conducted at any time during or after the study to ensure the validity and integrity of the study data.

8.8.2. Data Quality and Monitoring

In addition, the eCRF will include programmable edits to obtain immediate feedback if data are missing, out of range, illogical or potentially erroneous. Ad hoc queries will be generated within the eCRF and followed up for resolution.

High data quality standards will be maintained and processes and procedures utilised to repeatedly ensure that the data are as clean and accurate as possible when presented for analysis. Data quality will be enhanced through a series of programmed data quality checks that automatically detect out-of-range or anomalous data.

8.9. Limitations of the Research Methods

Potential limitations of the study design and measures proposed to address them include enrolment bias. To address this, sites will be expected to consecutively enrol eligible subjects and to maintain screening logs of all subjects meeting eligibility criteria, along with reasons for non-enrolment.

The Marketing Authorization Holder will closely monitor the enrolment rates. If projected enrolment rates indicate that patient targets may not be achieved within the planned enrolment period, consideration will be given to initiate additional sites within the participating countries, and/or to expand the study into additional EU countries.

Data collection will be initiated following the study-defined abstraction starting date. Initiation of selection of patient records meeting study selection criteria will commence on or following this date- September 2014. Data on drug utilisation will be censored from then and not considered in the analyses. This approach will ensure that study procedures do not influence prescribing practices.

A number of measures will also be implemented to ensure the completion of the drug utilisation questionnaire is conducted in a systematic, professional, and unbiased manner:

- Programming of the EDC version of the questionnaire (eCRF) will be reviewed by a quality control process and simulation prior to implementing the questionnaire
- Standard scripts will provide consistent instruction on completion of the questionnaire All individuals performing abstraction of data from medical records will be trained on appropriate data abstraction techniques

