This is a multi-national, multi-center study involving the retrospective review of approximately 300 to 450 patient medical records from selected European countries including France, Germany, Spain and possibly other countries, with each country having approximately six or seven sites. It is estimated that 18 to 21 hospital or office based sites overall, where prescribers of REVOLADE have been identified and medication records exist, will be targeted for recruitment. The investigators will be queried to identify REVOLADE-treated patients during the periods of interest. To meet the recruitment goal, additional EU country(ies) and sites may be added based on multiple factors including use of REVOLADE (compared to use approximated by sales data), available prescription data, market uptake, and favorable regulatory environment to conduct observational studies.

Medical records of all consecutive patients treated with REVOLADE, irrespective of indication, dose, treatment duration or any patient characteristic will be reviewed from first prescription of REVOLADE. This study is retrospective and therefore involves no intervention and will not impact the usual medical care nor affect the treatment of patients. The study will thus reflect real world medical practice without the potential for prescriber response bias which may occur in prospective studies (i.e., the Hawthorne Effect) (Mangione-Smith, 2002).

Study population:

Inclusion criteria

- Documented past treatment with REVOLADE (i.e., dispensed at least once by the pharmacy and patient received at least one dose) for whatever reason
- Patient (or a legal representative) has provided a written informed consent to participate in the study

Exclusion criteria

• Patients who participated or are participating in a randomized REVOLADE clinical trial

Variables

The following data will be collected for all patients enroled:

• Date of informed consent

The following data will be collected from *the medical records* for all patients enroled:

- Demographics [age at time of first REVOLADE prescribed dose, gender, race/ethnicity (where allowed by local regulation)]
- Primary diagnosis
- Medical history for applicable conditions and current medical conditions
- Treatment(s) preceding REVOLADE prescription (type, date, dose and duration)
- Concomitant treatment(s) with REVOLADE (type, date, dose and duration)

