8. RESEARCH METHODS

8.1. Study Design

This is a multi-national, multi-center study involving the retrospective review of approximately 300 to 450 patient medical records from selected European countries including France, Germany, Spain, and other relevant selected European Union (EU) Member States (see Section 8.2) with each country contributing approximately six or seven sites. It is estimated that 18 to 21 hospital or office based sites overall where prescribers of REVOLADE have been identified and medication records exist, will be targeted for recruitment. The investigators will be queried to identify REVOLADE treated patients during the periods of interest. To the extent possible, a selection of sites representative of the country prescription volumes will be enroled.

Medical records of all consecutive patients treated with REVOLADE, irrespective of indication, dose, treatment duration or any patient characteristic will be retrospectively reviewed to confirm eligibility.

Medical records will be reviewed for data from REVOLADE first prescription. This study involves no intervention, and will not impact the usual medical care or affect the treatment of patients. Thus, the study will reflect a real world medical practice without the potential for prescriber response bias, which may occur in prospective studies (i.e., the Hawthorne Effect) (Mangione-Smith, 2002).

The study overview is provided in the figure below:

[figure not shown]

Figure 1 REVIEU Study Overview

In Figure 1 EU approval for first indication (March 2010) refers to the approval of REVOLADE: "Revolade is indicated for adult chronic immune (idiopathic) thrombocytopenic purpura (ITP) splenectomised patients who are refractory to other treatments (e.g. corticosteroids, immunoglobulins). Revolade may be considered as

Page 116 WEUKBRE7133

second line treatment for adult non-splenectomised patients where surgery is contraindicated."

EU approval for second indication refers to "Revolade is indicated in adult patients with chronic HCV infection for the treatment of thrombocytopenia, where the degree of thrombocytopenia is the main factor preventing the initiation or limiting the ability to maintain optimal interferon-based therapy."

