Given the prescription rates of REVOLADE in EU Member States, a multi-faceted approach will be taken to identify potential sites and investigators. This approach will include the review of the CRO internal database, and the collaboration with GSK local operating companies on most suitable sites and market research of prescription data. A Site Qualification Survey will be administered to all identified potential sites requesting information on their location, practice (specialty, type), patients treated with REVOLADE within their practice (past and current number, treating duration) and dispensing system (not specifically related to the main objective of the DUS).

Based on responses from the Site Qualification Survey, a probability sample of REVOLADE prescribers will be selected, using a stratified unbiased random approach to produce a representative set of sites. This will ensure both representativeness and comprehensiveness of the sample in terms of types of REVOLADE prescribers. The general aim of this approach is to minimize biases such as for instance the recruitment of prescribers from academic versus community hospitals.

In order to ensure adequate numbers of participating sites, the Potential Prescriber List will include three times the number of sites required for the study. Depending on the participation rate and enrolment rates for the Study, the Back-up Potential Prescriber List of study sites may be contacted. To maximize representativeness at the study level, quota sampling of the remaining sites from the list will be performed.

The dispensing system of REVOLADE in the selected Member States is fully described in the ANNEX 2.

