8.2.5. Patient Enrolment

Since the purpose of this study is to evaluate routine clinical use of REVOLADE, patients will be identified based on the prescription of REVOLADE rather than on a specific diagnosis or condition.

The study population will consist of patients who have been prescribed REVOLADE for whatever reason according to the data retrieved in the medical records, provided they gave informed consent, had not or were not currently participating in a REVOLADE clinical trial, and used REVOLADE within the time period defined below. The medical records of all patients treated with REVOLADE in a participating centre will be reviewed for inclusion in this retrospective study, until the overall target number of at least 300 patients has been reached, irrespective of indication, medical condition, dose and treatment duration.

Patients are eligible for inclusion in study if their first prescription of REVOLADE was given between the period immediately after REVOLADE launch date and the start date for data abstraction i.e., September 2014. Patients who have been first prescribed REVOLADE after September 2014 will not be included in the study in order to ensure that study procedures do not influence prescribing practices. Informed consent will be

obtained as per country-specific regulations. Assuming the country-based first launched dates of REVOLADE in its initial chronic ITP indication (see Figure 1), the eligibility periods in the three selected countries thus span between January 2011 and September 2014 for France, April 2010 and September 2014 for Germany and December 2010 and September 2014 for Spain.

The earliest launch date for the chronic HCV-associated thrombocytopenia indication in these countries can be no sooner than September 2013, corresponding to the date it was approved by the European Commission. Considering that approval of HCV-associated thrombocytopenia indication was just recently, the number of expected HCV-associated thrombocytopenia patients therefore will be very small.

It is expected that approximately six or seven sites will be identified per country, and that up to 50 medical records will be abstracted at each site accounting for a total of 300 to 450 patients for the study.

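### The September 2014 cut-off follows the start of abstraction, not the date a site learns of the study, so it limits rather than rules out influence on prescribing

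*Protocol*

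**What the plan says.** **The cut-off.** Protocol 8.2.3 runs eligibility "until the index date chosen as the start date of data abstraction i.e., September 2014". Section 8.2.5 adds: "Patients who have been first prescribed REVOLADE after September 2014 will not be included in the study", and gives the protection of prescribing from study procedures as the reason. Section 8.9 says: "Data on drug utilisation will be censored from then and not considered in the analyses", and concludes: "This approach will ensure that study procedures do not influence prescribing practices".

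**The wider assurance.** Section 8.1 states that "the study will reflect a real world medical practice without the potential for prescriber response bias". The abstract says the same: "without the potential for prescriber response bias which may occur in prospective studies".

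**What happens at sites beforehand.** Section 8.2.4: "A Site Qualification Survey will be administered to all identified potential sites requesting information on their location". The survey also covers type of practice, dispensing system, and the past and current number of REVOLADE patients with their treatment duration. Sites are then drawn from the responses. The same section says the data will serve to judge whether prescribing follows the product labelling. Section 9 requires the investigator to sign agreement to the protocol before study start, and 9.3 requires ethics approval before enrolment at a site. Section 8.8.1: "During the site initiation visit, the monitor will provide training on the conduct of the study to the investigator".

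**Dates.** Section 5 plans sign-off for May 2014, registration for June 2014 and first patient in for September 2014. No date is given for the survey, the selection, receipt of the protocol at a site, or the initiation visit.

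**The concern.** The cut-off is the only mechanism offered for the claim that the study leaves prescribing untouched, and it is anchored to the wrong event. Abstraction is the last step of site start-up. A prescriber can learn of the study, and of its aim, at any of the steps before it. First prescriptions written between that moment and September 2014 enter the analysis as uninfluenced practice. For patients still on treatment, dose changes and discontinuations in that stretch are analysed too.

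Off-label use is the proportion on which the study is sized (8.5.1). Its classification in 8.3.4 depends on charted facts such as a contraindication for surgery, prior therapy, and thrombocytopenia limiting interferon-based therapy. If awareness changed prescribing or charting, the plausible direction is towards the label, which would lower the estimate. What is at stake is mainly an absolute assurance to the regulator that the design does not support.

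**Working it through.** **Step 1. Order of events at a site that enrols in September 2014.**

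- Survey, then selection from the responses (8.2.4).
- Ethics approval before enrolment at the site (9.3).
- Investigator's signature on the protocol before study start (9). That protocol contains the label-checking aim (8.2.4).
- Signed patient consent before any data are collected (9.1).
- First patient in, September 2014 (5). This is also the eligibility and exposure cut-off (8.2.3, 8.2.5, 8.9).

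At such a site, the first three steps fall before the cut-off. This follows from the required order alone and does not depend on the undated initiation visit.

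**Step 2. Length of the windows.** Months from launch (8.2.3), or from HCV approval (8.2.5), to September 2014:

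- Germany, from April 2010: 4 × 12 + 5 = 53
- Spain, from December 2010: 4 × 12 − 3 = 45
- France, from January 2011: 3 × 12 + 8 = 44
- HCV, from September 2013 at the earliest: 12

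**Step 3. Exposed share of each window.** Share = lead time / window length. The lead time is an assumption. Four months corresponds to sign-off in May and three to registration in June; one month represents a short start-up.

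| Lead | Germany | Spain | France | HCV |
|---|---|---|---|---|
| 1 month | 1/53 = 1.9% | 1/45 = 2.2% | 1/44 = 2.3% | 1/12 = 8.3% |
| 3 months | 3/53 = 5.7% | 3/45 = 6.7% | 3/44 = 6.8% | 3/12 = 25.0% |
| 4 months | 4/53 = 7.5% | 4/45 = 8.9% | 4/44 = 9.1% | 4/12 = 33.3% |

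**Step 4. The plan's own precision.** Section 8.5.1 gives 2.1% for a 5% rate at 400 patients. The normal-approximation half-width is 1.96 × √(0.05 × 0.95 / 400) = 0.0214, with limits 0.0286 and 0.0714. This reproduces the stated 2.1%, 2.9% and 7.1%.

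**Step 5. Bound on the overall effect.** Take the largest country share (9.1%) for every country, treat every site as on schedule, assume uniform accrual and a 5% off-label rate, and let awareness turn every off-label start in the exposed stretch into an on-label one. The proportion falls by 0.05 × 0.0909 = 0.0045, from 5.0% to about 4.55%. That is 0.45 points, about a fifth of the half-width (0.45/2.1 = 0.21). If twice as many patients started late as uniform accrual implies, the fall is 2 × 0.45 = about 0.9 points, still under half of it. The fall is proportional to the assumed off-label rate.

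**The case against.** The strongest case on the other side is that most of each 44-53 month window lies before any plausible site contact, so the contrast with a prospective study is largely right and the effect on the estimate is small. That stands, and it limits the point to a minor one.

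Several stronger readings are tempting, and the documents do not support them:

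- A reader might infer that all sites are surveyed, selected and trained before September 2014. Training is undated (8.8.1), 8.2.3 counts start-up together with data collection, and 8.2.3, 8.2.4 and 8.9 allow sites to be contacted or added later. Such sites may have had no contact before the cut-off.
- A reader might infer that a prescriber knows of a label check from first contact. The survey contents listed in 8.2.4 include nothing on indication, age, splenectomy, prior therapy or label status. Knowledge of that aim is firm only from receipt of the protocol.
- A reader might take the 25-33% for HCV as a measure of bias. It is calendar time under a 3-4 month assumption, in a group that 8.2.5 expects to be very small.

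It can also be said that a sensitivity analysis belongs in the analysis plan, which is not at hand. Its absence is not criticised here. But the site-level date has to be collected for such an analysis to be possible, and the eligibility rule and the assurance are protocol text.

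**Conclusion.** The point holds, and it is minor. The cut-off excludes influence from abstraction itself, but it cannot ensure that study procedures as a whole leave prescribing unaffected. At sites enrolling on schedule, prescribers have been surveyed and selected and have signed the protocol while their first prescriptions still count. The absolute statements in 8.9, 8.2.5, 8.1 and the abstract are therefore not properties of this design.

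With an assumed lead of one to four months, about 2-9% of the country windows and 8-33% of the HCV window is exposed. The effect on the overall off-label proportion is at most about 0.45 points, given a 5% rate, uniform accrual and a lead of no more than four months. Neither the lead time nor the existence of any response is documented, and nothing here invalidates the study.

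**What to change.** 1. Keep September 2014 as the cut-off for both eligibility and exposure data.
2. Record for each site the date of first study contact (survey sent) and the date the protocol was received.
3. Where that date precedes the cut-off, report the off-label proportion with and without patients first prescribed on or after it. Use first contact for the main split; protocol receipt gives the narrower one. The treatment start date is already collected (8.3.3).
4. Reword 8.1, 8.2.5, 8.9 and the abstract to say that the cut-off limits, rather than rules out, influence on prescribing.

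If an earlier eligibility date is preferred, define it per site as the earlier of the day before first contact and September 2014. Without that rule, a site first contacted after September 2014 would admit patients whom 8.2.5 excludes and who have no analysable exposure. This alternative also gives up part of the HCV window, which is already sparse.

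**Cost.** Two dates for each of the 18-21 sites, one extra table and a few changed sentences. The with/without comparison loses no patients.
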